##### **Infusion-related reactions (IRRs)**

Administration of monoclonal antibodies (mAbs) can be associated with IRRs. A focused search for potentially “severe” IRRs (i.e. indicative of hypersensitivity/anaphylaxis or cytokine-release syndrome) identified 3 (2.7%) patients treated with crizanlizumab 5 mg/kg in the pooled data set. The event reported for all 3 patients was “infusion-related reaction”, none of which was severe (all Grade 1 or 2, all non-serious), none required hospitalization or treatment discontinuation, and all events resolved without sequelae or complications on the same day.

However, severe IRRs including cases requiring hospitalization have been described in ongoing clinical trials and the post-marketing setting. Refer to Investigator's Brochure for additional details regarding these IRRs.

Additionally, a broad search for IRRs using an extensive list of potential signs and symptoms related to infusion reactions, and occurring within 24 hours of the infusion, identified 37 patients (33.3%) in the safety pool with at least one event. Most of these events were reported in 1 or 2 patients only, except for nausea (9.0%), headache (9 %), arthralgia (6.3%), back pain (4.5%), and fatigue, hypertension, dizziness, and myalgia (2.7%). None of the events were Grade 3 or 4 in severity. In the SUSTAIN study, IRRs using this broader search were more frequent in the 5 mg/kg arm (34.8%) compared to the placebo arm (21.0%). However, except for nausea, none of the events were reported with an absolute difference of more than 5% in the crizanlizumab 5 mg/kg vs. the placebo arm and none were severe. Based on post marketing reports, IRRs may present as pain, refer to Investigator's Brochure for additional details.

In summary, current data suggest that administration of crizanlizumab can be commonly associated with infusion related reactions, some of which can be severe and/or require hospitalization. Patients should be monitored for potential signs and symptoms of IRRs, and subjects instructed to contact the investigator/site when experiencing such events. In case of severe IRRs (eg. hypersensitivity/anaphylactic reaction), study treatment should be discontinued.

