Grade 1  Mild transient reaction; infusion interruption not indicated; intervention not indicated	
Recommendation:
 

Continue study treatment and increase monitoring of vital signs as medically indicated until the subject is deemed medically stable in the opinion of the investigator.

Consider slowing infusion rate.

Grade 2  Therapy or infusion interruption indicated but responds promptly to symptomatic treatment (e.g., antihistamines, NSAIDS, narcotics, IV fluids); prophylactic medications indicated for <=24 hrs	
Recommendation:
 

Temporarily interrupt infusion and increase monitoring of vital signs as medically indicated until the subject is deemed medically stable in the opinion of the investigator.

Administer appropriate medical therapy (e.g. analgesics such as paracetamol /acetaminophen or NSAIDs and anti-histamines), as per local institutional guidelines and clinical presentation.

Steroids should be used with caution unless clinically indicated (e.g. management of hypersensitivity/anaphylaxis).

If symptoms resolve, restart infusion per investigator discretion at a slower rate under continuous observation. Ensure a minimum of 1 hour observation period prior to restarting the infusion.

Before restarting, administer premedication (e.g. analgesics such as paracetamol/acetaminophen or NSAIDs and anti-histamines within 1 hour prior to dosing) as per local institutional guidelines for prophylaxis of infusion related reactions, including subsequent infusions.

In case of recurring infusion reactions despite premedication and prolonged infusion, consider discontinuation of study treatment.

Grade 3 and 4 Prolonged (e.g., not rapidly responsive to symptomatic medication and/or brief interruption of infusion); recurrence of symptoms following initial improvement; hospitalization indicated for clinical sequelae Life-threatening consequences; urgent intervention indicated
	
Mandatory:
 

• Permanently discontinue study treatment.

---	---

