c Certain adverse events reported in the AE/SAE eCRF as Infusion Related Reactions will require the IRR eCRF to be completed.

d Local sampling for platelet assessment will be performed throughout the trial for all subjects.

e The date, number, and duration of the priapic events in the 14-week period prior to consenting will be captured in a separate CRF.

f Subjects who will receive commercially approved crizanlizumab approximately 4 weeks after their last dose of study treatment, do not need to complete the 105-day follow-up.

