### **8.2.2.3 Uncomplicated VOC**

An uncomplicated pain crisis is defined as an acute event of pain with no known cause for pain other than a vaso-occlusive event; and requiring treatment with a parenteral or oral opioids or other parenteral analgesic; but is NOT classified as an acute chest syndrome, hepatic sequestration, splenic sequestration, or priapism. The end of an uncomplicated pain crisis will be considered the resolution of acute pain, such that residual pain (or absence of any pain) is considered to be chronic, and the current pain medication regimen is considered to be for this chronic pain.

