### General considerations for VOC assessments

Associated conditions in SCD (e.g. intermittent or chronic pain due to ankle/leg ulcers, aseptic necrosis of bone or gout) should not be considered VOC events. Similarly, complications such as pulmonary, cardiac, or renal failure are not themselves to be considered. If such events precipitates VOC, the VOC event will be documented separately.

For each visit to a medical facility for a pain event thought to be a VOC, the following information must be documented in the eCRF; diagnostic evaluation for the event, subject treatment and management, course, duration of the crisis, and outcome. For subjects who are treated at medical facilities other than the study site, summary documents (e.g. ER or hospital discharge summaries) will need to be obtained.

Subjects should be encouraged to contact the investigator (or surrogate from the site) when they believe they are experiencing a VOC, which they believe they can manage at home, both for treatment guidance and for accurate information which may be obtained for the VOC eCRF page. VOCs and other acute pain crisis managed at home will be reconciled at regular study visits and captured in the corresponding VOC eCRF.

If a subject experiences a VOC surrounding a protocol-scheduled visit day, and the subject presents for this visit, it will be counted as a VOC that led to a healthcare visit (provided the event meets the criteria for VOC discussed above). VOC is not a known contra-indication, but dosing during a crisis should be at investigator's discretion.

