### 10.1.2 Protocol exempt AEs & SAEs

Protocol Exempt AEs & SAEs are implemented in the crizanlizumab program. VOCs must be reported on the VOC page in the eCRF. As VOCs are considered secondary endpoints for the purpose of evaluation of efficacy, AEs and SAEs involving VOCs SHOULD NOT be reported as AEs or SAEs for the purpose of this study. These events will not be considered as SAEs in regard to reporting requirements. Procedures which are directly related to the VOC, e.g. ventilation of a patient with acute chest syndrome are considered part of the VOC and will not be reported as AE/SAEs but entered in the CRF-page "concomitant non-drug therapies/procedures". Additional events or complications which are not VOCs itself will be reported as AE/SAEs. Details will be given in the CRF-completion guidance. In case that new information arises which changes the diagnosis of a VOC, i.e. gives another medically determined explanation than vaso-occlusion in the opinion of the investigator, the event has to be reported according to the rules of [Section 10.1](#) and must be reported to Novartis within 24 hours of learning of the new information.

The events in [Table 10-1](#) will not be reported as AEs/SAEs.

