2.7.1.1 Adverse events of special interest / grouping of AEs

Not applicable

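### Post-infusion pain of uncertain cause that is attributed to vaso-occlusion leaves the AE and IRR data, so infusion reactions may be undercounted and the on-treatment VOC rate raised

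*Protocol*

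**What the plan says.** Protocol 4.5 lists IRRs as a risk, mentions severe cases needing hospital care, and adds: "Based on post marketing reports, IRRs may present as pain, refer to Investigator's Brochure for additional details".

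Protocol 8.2.2.3 gives this definition of an uncomplicated VOC: "acute event of pain with no known cause for pain other than a vaso-occlusive event; and requiring treatment with a parenteral or oral opioids". Any analgesic given parenterally also satisfies its treatment part. Table 10-1 applies a similar test: there must be no other medically determined explanation. Neither definition mentions when the pain starts relative to an infusion. Protocol 12.5.1 says that uncomplicated VOCs are not adjudicated.

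For reporting, Protocol 10.1.2 sends VOCs to the VOC page and states that "AEs and SAEs involving VOCs SHOULD NOT be reported as AEs or SAEs for the purpose of this study". The same section keeps events that are not VOCs reportable. It also requires a report within 24 hours if new information changes the diagnosis of a VOC to another cause. It leaves details to a CRF-completion guidance.

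The only trigger described for the IRR form is footnote c of Table 8-1: "Certain adverse events reported in the AE/SAE eCRF as Infusion Related Reactions will require the IRR eCRF to be completed".

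In the SAP, section 2.7.1.1, "Adverse events of special interest / grouping of AEs", is marked as not applicable.

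**The concern.** In these patients, back, joint or muscle pain on an infusion day can plausibly be read either as a reaction to the drug or as a crisis. Treatment does not separate the two readings. Table 6-2 describes a Grade 2 IRR as one that "responds promptly to symptomatic treatment (e.g., antihistamines, NSAIDS, narcotics, IV fluids"), and narcotics also satisfy the treatment part of the VOC definition. Only the investigator's attribution decides, and that attribution then decides whether the event reaches the safety data at all.

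Two results are at stake. The first is the count of a named risk, in a trial whose secondary safety objective covers the number, seriousness and causality of adverse events. The second is the uncomplicated VOC rate, a secondary efficacy endpoint that could contain drug reactions. The trial has a single arm, so no control group would show the shift.

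**Working it through.** This is mainly a question of classification, so the first step is to follow one event through the rules. The second step shows what scale would matter.

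**Path of the event.** Take acute pain starting during or within hours of an infusion and treated with an opioid.

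1. *Recognised as an infusion reaction.* A cause other than vaso-occlusion is then known, so 8.2.2.3 and Table 10-1 are not met. Under 10.1.2 it is reported as an AE, and the IRR eCRF can open. There is no gap here.
2. *Cause uncertain, attributed to vaso-occlusion.* The VOC definition is met. The event goes to the VOC page and is barred from AE/SAE reporting, and without an AE entry footnote c does not apply. For facility visits, the VOC information listed in the general considerations for VOC assessments is evaluation, treatment, course, duration and outcome. Relationship to study drug, which 10.1.1 requires for an AE, is not listed.
3. *Attribution later revised.* The event returns to AE reporting, but only on new information. The infusion date is known from the outset, so it would not normally count as new.
4. *Analysis.* SAP 2.7.1 summarises AEs from the AE data, and 2.7.1.1 adds no IRR grouping. SAP 2.6.2 counts VOCs in the annualised rate without regard to infusion timing.

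Dosing visits are scheduled visits, and the protocol says: "If a subject experiences a VOC surrounding a protocol-scheduled visit day, and the subject presents for this visit, it will be counted" as a VOC leading to a healthcare visit. The sentence carries a proviso that the VOC criteria are met, so it classifies VOCs and does not itself turn undiagnosed pain into one.

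**The nearest stated figure.** The broad 24-hour IRR search in Protocol 4.5 found 37 of 111 patients: 37/111 = 33.3%, which reproduces. It shows that a 24-hour search has been used in this programme. It does not measure how often pain is recorded as VOC instead.

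**Illustrative scale.** Inputs:
- Infusions at Weeks 1, 3, 7 and every 4 weeks to 51 (Protocol 6.1): 14 per subject, 7 of them before Week 27.
- 36 subjects, so 14 × 36 = 504 infusions if all are given.
- Annualised rate = events × 365.25 / days (SAP 2.6.2), with 182 days to Week 26 and 364 to Week 52.
- q = share of infusions followed by a pain IRR recorded as VOC. This is an **assumption**; the documents give no value.

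One such event adds 365.25/182 = 2.01 per year to that subject's 26-week rate, or 365.25/364 = 1.00 to the 52-week rate. The mean rise is q × 7 × 365.25/182 = q × 14.05, and it is the same at 52 weeks (q × 14 × 365.25/364).

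| q (assumed) | Events missing from AE data (504 × q) | Rise in mean annualised VOC rate |
|---|---|---|
| 0 | 0 | 0 |
| 0.5% | 2.5 | 0.07 |
| 1% | 5.0 | 0.14 |
| 2% | 10.1 | 0.28 |
| 5% | 25.2 | 0.70 |

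**Direction.** The 12-week baseline contains no infusions, so any such error falls only on the treatment period. It favours the drug on IRRs and works against it on change in VOC rate.

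**The case against.** The strongest reply is that cause already separates the two categories. Both VOC definitions exclude pain with another known or medically determined explanation, non-VOC events are expressly reportable, and a re-diagnosed VOC must be reported within 24 hours. Protocol 4.5 also asks for monitoring for IRRs, Table 8-1 carries a continuous IRR row, and SAP 2.7.1 will show reported IRRs by preferred term, grade and relationship. All of this stands. It leaves open only pain of uncertain cause, for which the protocol and SAP give no time window and no required IRR assessment.

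A reader might infer several stronger things that the documents do not support:

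- *That pain IRRs as such meet the VOC definition and cannot reach the IRR form.* Recognised reactions fail the definition and remain reportable.
- *That the frequencies in Protocol 4.5 measure the loss.* They come from a safety-pool search and give neither opioid use nor a rate of VOC misclassification. The same section reports no Grade 3 or 4 events in the broad search. Although the search was positive in 34.8% against 21.0% on placebo, no single event except nausea differed by more than 5% between arms.
- *That the Grade 3/4 IRR treatment rule is bypassed.* Section 6.5 and Table 6-2 turn on the graded reaction, not on which CRF page was completed.
- *That the shift could never be detected.* VOC and infusion dates should allow a retrospective check.

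Finally, the CRF-completion guidance and the Investigator's Brochure are not among the documents and may contain a rule. If so, the protocol and SAP should cite it.

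**Conclusion.** The point holds as a gap in classification and analysis. The VOC exemption takes no account of infusion timing, so pain near an infusion that is attributed to vaso-occlusion is absent from every safety summary in the visible SAP. IRRs may be undercounted, and the on-treatment uncomplicated VOC rate may be raised.

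Confidence is high that the protocol and SAP contain this gap. Its size is unknown: the table in the working rests wholly on an assumed q, and the effect is zero if no event is misattributed. The VOC endpoint is summarised descriptively and the bias there would be against the drug. The primary endpoint (priapic events), the sample size, the power and the alpha are unaffected. The change is worth making because it is cheap, uses the programme's own 24-hour window, and makes a one-sided shift visible in a trial with no control arm.

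**What to change.** 1. **SAP 2.7.1.1.** Replace the not-applicable entry with an IRR summary: investigator-reported IRRs, plus a 24-hour post-infusion search (the window in Protocol 4.5) of both AE-page and VOC-page events. Use dates where times are missing. Show VOC-page events separately as possible IRRs and do not merge them into the reported count.
2. **SAP 2.6.2.** Present the uncomplicated VOC rate with and without events starting within 24 hours of an infusion.
3. **Protocol 10.1.2.** For any VOC starting within 24 hours of an infusion, require the investigator to record whether an infusion reaction is suspected. If it is, require reporting on the AE page and IRR eCRF, and as an SAE if serious. Do not enter every such VOC twice; that would overcount coincidental crises as reactions.

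The SAP items matter most. Enrolment was already closed at Protocol Amendment 3, so the protocol change has limited prospective value. The SAP items should need no new data: SAP 2.6.2 already counts VOCs over time windows, which requires dated events, and SAP 2.1.1 takes infusion dates from the administration record.

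The cost is two tables and a little data entry. Some coincidental crises will appear as possible IRRs, more so where only dates are available, and the IRR count may look less favourable.

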**Table 10-1 List of Events Not Requiring AE/SAE Reporting**

#### VOC Events

- Uncomplicated sickle cell-related pain crisis (SCPC) or vaso-occlusive crisis (VOC)\*
- Acute chest syndrome
- Hepatic sequestration
- Splenic sequestration
- Acute priapism requiring a visit to a medical facility

\*VOC is defined as pain crises (defined as an acute onset of pain for which there is no other medically determined explanation other than vaso-occlusion and which requires therapy with oral or parenteral opioids or parenteral NSAIDs) as well as other complicated crises, such as acute chest syndrome, acute priapism, and hepatic or splenic sequestration.

### 10.1.3 Serious adverse events

An SAE is defined as any AE [appearance of (or worsening of any pre-existing)] undesirable sign(s), symptom(s) or medical conditions(s)) which meets any one of the following criteria:

- fatal
- life-threatening

Life-threatening in the context of a SAE refers to a reaction in which the subject was at risk of death at the time of the reaction; it does not refer to a reaction that hypothetically might have caused death if it were more severe (please refer to the ICH-E2D Guidelines).

- results in persistent or significant disability/incapacity
- constitutes a congenital anomaly/birth defect
- requires inpatient hospitalization or prolongation of existing hospitalization, unless hospitalization is for:
  - routine treatment or monitoring of the studied indication, not associated with any deterioration in condition.

- elective or pre-planned treatment for a pre-existing condition that is unrelated to the indication under study and has not worsened since signing the informed consent
- social reasons and respite care in the absence of any deterioration in the subject's general condition
- treatment on an emergency outpatient basis for an event not fulfilling any of the definitions of a SAE given above and not resulting in hospital admission
- is medically significant, e.g. defined as an event that jeopardizes the subject or may require medical or surgical intervention to prevent one of the outcomes listed above

Medical and scientific judgment should be exercised in deciding whether other situations should be considered serious reactions, such as important medical events that might not be immediately life threatening or result in death or hospitalization but might jeopardize the subject or might require intervention to prevent one of the other outcomes listed above. Such events should be considered as "medically significant". Examples of such events are intensive treatment in an emergency room or at home for allergic bronchospasm, blood dyscrasias or convulsions that do not result in hospitalization, or development of dependency or abuse.

All malignant neoplasms will be assessed as serious under "medically significant" if other seriousness criteria are not met.

Any suspected transmission via a medicinal product of an infectious agent is also considered a serious adverse reaction.

All reports of intentional misuse and abuse of the product are also considered SAE irrespective if a clinical event has occurred.

#### **10.1.4 SAE reporting**

To ensure subject safety, every SAE, regardless of causality, occurring after the subject has provided informed consent and until up to 105 days after the subject has stopped study treatment must be reported to Novartis within 24 hours of learning of its occurrence. Detailed instructions regarding the submission process and requirements are to be found in the investigator folder provided to each site.

All follow-up information for the SAE including information on complications, progression of the initial SAE and recurrent events must be reported as follow-up to the original event within 24 hours of the investigator receiving the follow-up information. An SAE occurring at a different time interval or otherwise considered completely unrelated to a previously reported one must be reported separately as a new event.

Any SAEs experienced after the end of the safety evaluation follow-up period should only be reported to Novartis if the investigator suspects a causal relationship to the study treatment.

Each re-occurrence, complication, or progression of the original event should be reported as a follow-up to that event regardless of when it occurs. The follow-up information should describe whether the event has resolved or continues, if and how it was treated, whether the blind was broken or not, and whether the subject continued or withdrew from study participation.

Follow-up information is submitted in the same way as the original SAE Report and should describe whether the event has resolved or continues, if and how it was treated, and whether the patient continued or withdrew from study participation.

If the SAE is not previously documented in the Investigator's Brochure or Package Insert (new occurrence) and is thought to be related to the study treatment, a Novartis Chief Medical Office and Patient Safety (CMO & PS) Department associate may urgently require further information from the investigator for health authority reporting. Novartis may need to issue an Investigator Notification (IN) to inform all investigators involved in any study with the same study treatment that this SAE has been reported.

Suspected Unexpected Serious Adverse Reactions (SUSARs) will be collected and reported to the competent authorities and relevant ethics committees in accordance with EU Guidance 2011/C 172/01 or as per national regulatory requirements in participating countries.

#### **10.1.5 Pregnancy reporting**

Pregnancy outcomes should be collected for the female partners of any males who took study treatment in this study. Consent to report information regarding these pregnancy outcomes should be obtained from the mother. To ensure subject safety, each pregnancy occurring after signing the informed consent must be reported to Novartis within 24 hours of learning of its occurrence. The pregnancy should be followed up to determine outcome, including spontaneous or voluntary termination, details of the birth, and the presence or absence of any birth defects, congenital abnormalities, or maternal and/or newborn complications.

Pregnancy should be recorded and reported by the investigator to the CMO&PS. Pregnancy follow-up should be recorded on the same form and should include an assessment of the possible relationship to the study treatment any pregnancy outcome. Any SAE experienced during pregnancy must be reported.

